#### 9.3.2 30-Day Data Collection [REDACTED]

The following data collection will occur at 30 days post index procedure:

1. Clinical assessment with physical exam
2. NYHA classification (based on symptoms of any limitations)
3. Echocardiogram, including parameters noted above in Baseline.
4. If applicable, reintervention procedure details
5. Lab Measurements (CBC, Platelet count, and Creatinine)
6. Cardiovascular medications
7. Adverse events and protocol deviations related to safety reporting (if applicable)

#### 9.3.3 1-Year Data Collection [REDACTED]

The following data collection will occur at 1 year post-index procedure:

1. Clinical assessment with physical exam
2. NYHA classification
3. Echocardiogram, including parameters noted above in Baseline.
4. If applicable, reintervention procedure details
5. Cardiovascular medications
6. Adverse events and protocol deviations related to safety reporting (if applicable)

#### 9.3.4 2-Year Data Collection [REDACTED]

The following data collection will occur at 2 years post-index procedure:

1. Clinical assessment with physical exam
2. NYHA classification
3. Echocardiogram, including parameters noted above in Baseline.
4. If applicable, reintervention procedure details
5. Cardiovascular medications
6. Adverse events and protocol deviations related to safety reporting (if applicable)

#### 9.3.5 3-Year Data Collection [REDACTED]

The following data collection will occur at 3 years post-index procedure:

1. Clinical assessment with physical exam
2. NYHA classification
3. Echocardiogram, including parameters noted above in Baseline.
4. If applicable, reintervention procedure details
5. Cardiovascular medications
6. Adverse events and protocol deviations related to safety reporting (if applicable)

**9.3.6 4-Year Data Collection**

The following data collection will occur at 4 years post-index procedure:

1. Clinical assessment with physical exam
2. NYHA classification
3. Echocardiogram, including parameters noted above in Baseline.
4. If applicable, reintervention procedure details
5. Cardiovascular medications
6. Adverse events and protocol deviations related to safety reporting (if applicable)

**9.3.7 5-Year Data Collection**

The following data collection will occur at 5 years post-index procedure:

1. Clinical assessment with physical exam
2. NYHA classification
3. Echocardiogram, including parameters noted above in Baseline.
4. If applicable, reintervention procedure details
5. Cardiovascular medications
6. Adverse events and protocol deviations related to safety reporting (if applicable)

**Table 3: Data Collection Overview**

Visit Activity or Information Collected	Initial Data Collection			Follow-Up Data Collection					
	Baseline	Procedure	Discharge	30-Day	1 Year	2 Year	3 Year	4 Year	5 Year
Demographics	X								
Medical History	X								
Lab measurements*	X			X					
Clinical Assessment with physical exam ^			X	X	X	X	X	X	X
Cardiovascular Medications (examples: cardiac medications and blood thinners)	X			X	X	X	X	X	X
NYHA Classification β	X			X	X	X	X	X	X
Transthoracic Echocardiography (TTE) or Transesophageal Echocardiography (TEE) γ	X		X	X	X	X	X	X	X
Procedure details		X							
Adverse Events, Device Deficiency, and Withdrawal Σ		X	X	X	X	X	X	X	X
Reintervention Procedure (if applicable)			X	X	X	X	X	X	X
Protocol Deviations related to informed consent process or inclusion/exclusion criteria, or safety reporting requirements (if applicable)	X	X	X	X	X	X	X	X	X

\*Blood tests that are standard of care; βNYHA will be determined from signs and symptoms observed attributed to heart function and can be calculated from medical records. ^Clinical assessment will assess general health and information on any new diagnostics, treatments, or tests since the last visit. ΣIf applicable; γEchocardiograms submitted to the Echo Core Lab should be imaging medium but may be provided as a report if imaging is not available to submit to the core lab.

Note: Neurologic assessments will be collected for any neurologic event (if applicable) and may be assessed from available medical records.

In the event that more than 1 echocardiogram or required data point is performed and available within a specific study data collection timepoint, the data closest to the study timepoints will be used for the primary analysis. However, all available data should be collected in additional applicable CRFs. Additional echocardiograms should be submitted to the echocardiogram core lab for analysis. Data may be collected based on availability from SOC and protocol deviations for out of window/missed visit or out of window/missed data will not be required.

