**Figure 2: Study Flow Chart**

\*Echocardiogram imaging to include comprehensive TTE or TEE 2D echocardiogram, including, at minimum, assessment of aortic valve gradients (mean gradient, peak jet velocity, or doppler velocity index (DVI), aortic valve area (AVA), indexed effective orifice area (EOA), indices, degree of regurgitation- paravalvular leak (PVL), cardiac output and cardiac index, left ventricle systolic function (global and segmental). Echocardiogram imaging studies must be submitted to Abbott when available. If not available, echocardiogram imaging reports may be acceptable.

\*\*Including CBC, Platelet count, BUN, creatinine and/or estimated GFR

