#### **4.2 Additional echocardiogram and data available**

In the event that more than 1 echocardiogram or required data point is performed and available within a specific study data collection timepoint, the data closest to the study timepoints will be used for the primary analysis. However, all available data should be collected in additional applicable CRFs. Additional echocardiograms should be submitted to the echocardiogram core lab for analysis.

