### 9.1 Baseline

The following baseline (pre-ViV implant procedure) data will be collected from medical records for all enrolled subjects:

1. Medical History
2. Demographics
3. Cardiovascular medications
4. New York Heart Association (NYHA) Classification (based on symptoms of any limitations)
5. Echocardiography to include comprehensive transthoracic (TTE) or transesophageal (TEE) 2D echocardiogram, including, at minimum, assessment of aortic valve gradients (mean gradient, peak jet velocity, or doppler velocity index (DVI), aortic valve area (AVA), indexed effective orifice area (EOA), indices, degree of regurgitation, cardiac output and cardiac index, left ventricle systolic function (global and segmental).  
*For all data-collection timepoints, echocardiogram reports may be acceptable if imaging study is not available to be submitted to Abbott.*
6. Lab Measurements per SOC (including CBC, Platelet count, BUN, creatinine and/or estimated GFR)
7. Protocol deviations related to informed consent process or, inclusion/exclusion criteria (if applicable)

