The following definitions of HVD Stages (1-3) will be used when assessing valve integrity.

- Stage 1 (Morphological Valve Deterioration): Evidence of SVD, non-structural valve dysfunction (other than paravalvular or PPM), thrombosis or endocarditis without significant hemodynamic changes.
- Stage 2 (Moderate hemodynamic valve deterioration): Increase in mean transvalvular gradient ≥10 mmHg resulting in mean gradient ≥20 mmHg with concomitant decrease in EOA ≥0.3 cm^2 or ≥25% and/or decrease in Doppler velocity index ≥0.1 or ≥20% compared with echocardiographic assessment performed 1-3 months post-procedure, OR new occurrence or increase of ≥1 graded of intra-prosthetic AR resulting in ≥ moderate AR
- Stage 3 (Severe hemodynamic valve deterioration): Increase in mean transvalvular gradient ≥20 mmHg resulting in mean gradient ≥30 mmHg with concomitant decrease in EOA ≥0.6 cm^2 or ≥50% and/or decrease in Doppler velocity index ≥0.2 or ≥40% compared with echocardiographic assessment performed 1-3 months

post-procedure, OR new occurrence, or increase of ≥2 grades, of intra-prosthetic AR resulting in severe AR.

• Any need for Portico TAVI re-intervention after implant through 5 years

6. Clinical benefit endpoints defined as improvement from baseline to 30 days, 1 year, and annually through 5 years from index procedure, including:

• New York Heart Association (NYHA) functional classification

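### Echo values are selected by date whether TTE or TEE, so valve deterioration near the 10 and 20 mmHg thresholds can be staged on mixed-modality pairs

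*Protocol*

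**What the plan says.** **Modality.** Protocol Table 3 lists "Transthoracic Echocardiography (TTE) or Transesophageal Echocardiography (TEE" at baseline, discharge, 30 days and years 1 to 5. Protocol 9.1, to which each follow-up list in 9.3 refers back, asks for a "comprehensive transthoracic (TTE) or transesophageal (TEE) 2D echocardiogram, including, at minimum, assessment of aortic valve gradients", followed by DVI, AVA and indexed EOA. The note to Figure 2 says the same. Either modality may supply the Doppler values.

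**Selection.** When a timepoint has more than one echo, protocol 4.2 says that "the data closest to the study timepoints will be used for the primary analysis", and the note to Table 3 repeats this. Modality is not a criterion. All additional echoes are still collected and sent to the core laboratory.

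**Use.** SAP 1.4.3 (as protocol 5.3) defines Stage 2 by "Increase in mean transvalvular gradient ≥10 mmHg resulting in mean gradient ≥20 mmHg with concomitant decrease in EOA" or DVI, and Stage 3 by "Increase in mean transvalvular gradient ≥20 mmHg resulting in mean gradient ≥30 mmHg with concomitant decrease in EOA" or DVI with larger falls, each "compared with echocardiographic assessment performed 1-3 months" after the procedure. A separate route to each stage runs through regurgitation grade. Nothing requires the two echoes to share a modality.

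**Analysis.** SAP 2.3.2 summarises the descriptive endpoints on available data. SAP 2.11 adjusts for no covariates unless otherwise specified. The sensitivity analyses in SAP 2.12 concern the primary endpoints only. No split by modality is planned, so pooling of TTE and TEE values follows from that absence; it is not stated outright.

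**The concern.** A within-patient change score is free of measurement offset only if both measurements carry the same offset. Here a selection rule that is written down, not merely a silence, can put a TEE value where a TTE value was also available, at either end of the difference. The offset then goes into a change that is compared with a fixed 10 or 20 mmHg cut.

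TEE use is also unlikely to be random. The VARC-3 thrombosis definition in protocol Appendix B counts TEE findings as confirmatory imaging, and echoes are collected as standard of care provides them. It is a reasonable inference, though the documents do not say so, that follow-up TEEs cluster in patients with suspected valve dysfunction, whom the staging is meant to classify.

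At stake are the haemodynamic summaries (descriptive endpoint 4) and gradient-route HVD staging (descriptive endpoint 5). SAP 1.3 plans up to 100 patients in the primary analysis population. One reclassified patient is then at least 1/100 = 1 percentage point of an HVD rate, and more if fewer patients have paired echoes.

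**Working it through.** The plan gives no figure to reproduce. The check applies the Stage 2 gradient route to an assumed modality effect.

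**From the documents:** Stage 2 needs a rise in mean gradient of at least 10 mmHg, a resulting gradient of at least 20 mmHg, and a fall in EOA (at least 0.3 cm² or 25%) and/or in DVI (at least 0.1 or 20%).

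**Assumed:** f is the ratio of TEE to TTE valve jet velocity, with the outflow-tract term unchanged. Recorded gradient = true gradient × f²; recorded DVI and EOA = true value ÷ f. Reference DVI is 0.40 and EOA 1.4 cm². Flow is constant, so true DVI and EOA scale with 1/√gradient. TTE is taken as the truth.

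**1. TTE reference, TEE follow-up, f < 1 (hides a rise)**
- 12 to 24 mmHg, f = 0.95: 24 × 0.9025 = 21.7, rise 9.7. Stage 2 missed.
- 12 to 26, f = 0.90: 26 × 0.81 = 21.1, rise 9.1. Missed.
- 15 to 28, f = 0.90: 28 × 0.81 = 22.7, rise 7.7. Missed.
- 12 to 35, f = 0.80: 35 × 0.64 = 22.4, rise 10.4. Still Stage 2.

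With a reference of 12, the true follow-up gradient must reach 22/f² rather than 22: 24.4 at f = 0.95 and 27.2 at f = 0.90. The band of hidden cases is therefore 2.4 or 5.2 mmHg wide.

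**2. TEE reference, TTE follow-up, f < 1 (creates a rise)**
- 13 to 21 mmHg, f = 0.90: reference 13 × 0.81 = 10.5, rise 10.5. DVI goes from 0.40/0.90 = 0.444 to 0.40 × √(13/21) = 0.315, a fall of 29%. Stage 2 created.
- The same change, f = 0.95: reference 11.7, rise 9.3. Not created.

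**3. No true change, TEE reference.** A false Stage 2 at gradient G needs G(1 − f²) ≥ 10: f ≤ 0.707 at 20 mmHg, 0.774 at 25 and 0.816 at 30. At 15 mmHg it is impossible, because the 20 mmHg floor is not met.

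**4. Opposite direction.** If TEE read 5% high at follow-up, 13 to 21 would be recorded as 21 × 1.1025 = 23.2, a rise of 10.2, with DVI falling from 0.40 to 0.315/1.05 = 0.300 (25%). Stage 2 is created. The sign of the offset decides which error occurs, not whether one can.

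**5. Same-modality pairs.** TTE–TTE pairs carry no offset. In a TEE–TEE pair a fixed mmHg offset cancels from the rise. A proportional one cancels in part: 12 to 24 at f = 0.95 is recorded as 10.8 to 21.7, a rise of 10.8, which keeps Stage 2.

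**6. Fixed-offset view of the 10 mmHg limb alone.** Assume TEE reads 5 mmHg low (range 3 to 8) and the SD of a measured change is 5 mmHg. P(measured rise ≥ 10) = Φ((true rise ± offset − 10)/5).
- True rise 12: Φ(0.4) = 66% with TTE at both visits; Φ(−0.6) = 27% (42% to 12%) with TEE at follow-up.
- True rise 6: Φ(−0.8) = 21%; Φ(0.2) = 58% (42% to 79%) with TEE as reference.

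These are not Stage 2 rates, because the 20 mmHg floor and the EOA/DVI condition are left out.

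**7. Visit means.** If 5% to 15% of readings are TEE (assumed), the mean gradient shifts by 0.05 × 3 = 0.15 to 0.15 × 8 = 1.2 mmHg.

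**The case against.** The case against is substantial.

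- **The offset is not in the documents.** Its size, its direction and the frequency of TEE are all assumed. This stands: the point is conditional on a systematic difference existing.
- **The fixed-offset figures are generous.** At a 12 mmHg reference, reading 5 or 8 mmHg low implies a velocity ratio of √(7/12) = 0.76 or √(4/12) = 0.58, that is 24% or 42% low. This stands too, and the proportional model is the better guide.
- **Stage 2 needs more than a gradient rise.** True, but the EOA/DVI condition protects only partly, because all three measures share the valve jet velocity and move together.
- **A core laboratory reads the echoes** to American Society of Echocardiography and VARC standards (protocol synopsis). It may have its own modality convention, and the CRF may already record modality; neither is in the documents. However, reports may stand in for images, and rereading cannot remove a difference already in the recording.
- **Protocol 4.2 selects among echoes or data points**, so a TEE without a usable gradient need not displace a TTE gradient. That is fair. A TEE with one still can.
- **Other measures of valve function remain:** regurgitation grade, morphology, thrombosis, endocarditis and re-intervention. A TEE done for suspected endocarditis would not lose the event, only perhaps its stage.
- **If TEE is mostly done for cause, a TEE reference at 1 to 3 months should be uncommon,** which weakens the route that creates a rise.

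A reader might infer from the words on the primary analysis in protocol 4.2 and 4.3 that the primary endpoints are exposed. They are not: both are clinical composites adjudicated by the events committee and use no echo value.

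**Conclusion.** The gap is real and small: a cheap improvement, not an analysis error. The date-only rule and the absence of a same-modality requirement let any systematic TTE/TEE difference misclassify patients near the 10 or 20 mmHg thresholds. Under the assumed model, a 5% to 10% velocity difference is enough to do so. Stage 2 in a wholly stable valve at 20 to 30 mmHg would need roughly an 18% to 29% difference. Stage 3 and the regurgitation route were not modelled; Stage 3 shares the same structure.

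Two stronger readings are tempting and unsupported. One is that the HVD rate is biased in a known direction: the documents give no direction, and the error depends on which of the two echoes is the TEE. The other is that valve function as a whole becomes unmeasurable: only the Doppler values within descriptive endpoints 4 and 5 are exposed, and the assumed shift in visit means is at most 1.2 mmHg.

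**What to change.** In protocol 4.2 (with the matching note to Table 3) and SAP 2.3.2:

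1. When both a TTE and a TEE exist at a timepoint, including the 1 to 3 month reference, take mean gradient, EOA/AVA, iEOA and DVI from the TTE closest to the timepoint. Use TEE for these values only when no TTE exists.
2. Record the modality of each echo, if the CRF does not already do so.
3. Derive gradient-route HVD primarily from same-modality pairs. Keep and flag mixed pairs, and report HVD with and without them.

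Restricting staging to TTE–TTE pairs would be the wrong trade. It would leave TEE-only subjects unstaged by gradient, possibly those with suspected valve failure, in a plan that imputes nothing (SAP 2.8). It would also discard TEE–TEE pairs, in which the offset cancels wholly or in part.

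Cost: wording in two documents, possibly one CRF field, and one extra tabulation. The TTE used may lie somewhat further from the nominal timepoint than the TEE it replaces. No new patient procedure is needed, since the additional echoes are already collected.

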#### **9.4 Subject Study Completion**

Subject participation in the study will conclude when:

1. The subject completes the 5-year data collection time point.
2. When consent is withdrawn (by the subject or legal authorized representative).
3. When the subject is deceased at the time of enrollment or dies during the study, their study completion will occur after their last study follow-up was available, including details of what led up to death and the cause of death.
4. When the subject is lost to follow-up, their study completion will occur after their last study follow-up.
5. For subject's where the Portico delivery system entered their body but was not successfully implanted, they will complete the study after 30 days from the attempted procedure.

Upon completion of subject participation in this data-collection study, the subject will continue to receive follow-up as per standard of care.

#### **9.5 Description of Activities Performed by Sponsor Representatives**

Trained Sponsor personnel may provide guidance to ensure compliance to the protocol. If applicable, they may provide technical expertise and technical guidance related to the protocol. While Sponsor representatives may perform these activities, the Principal Investigator remains responsible for ensuring all study data is collected as required per the protocol.

### **10 CORE LABORATORY**

#### **10.1 Echo Core Laboratory**

Echocardiographic examinations will be forwarded to an independent Echocardiographic Core Laboratory for interpretation. It is the responsibility of each study site to perform the local interpretation of the echocardiogram for clinical assessment. The Echocardiographic Core Laboratory will not be responsible for notifying the site of any abnormal findings that are identified as part of participation in the study.

The responsibility of the Echocardiographic Core Laboratory is to complete the data collection forms and provide the study required interpretation and documentation of each echocardiogram submitted to the Sponsor. Data obtained from the Core Laboratory evaluation will be used for study purposes only and not for clinical treatment of the subject.

## 11 SAFETY REPORTING

To comply with worldwide standards and guidelines on clinical investigation adverse event reporting, the Sponsor has adopted uniform and worldwide applicable standard definitions and reporting timelines to be used and adhered to by the investigators.

### 11.1 Adverse Events

An adverse event (AE) is any untoward medical occurrence, unintended disease or injury, or untoward clinical signs (including abnormal laboratory findings) in subjects, users or other persons, whether or not related to the medical device under investigation.

As part of ISO14155 Section 3.2, the Adverse Event definition includes notes outlined below.

**Note 1:** This definition includes events related to the medical device under investigation or the comparator.

**Note 2:** This definition includes events related to the procedures involved.

**Note 3:** For users or other persons, this definition is restricted to events related to medical devices under investigation.

### 11.2 Serious Adverse Event (SAE)

If the AE meets any of the criteria below, it is regarded as a serious adverse event.

1. Led to a death,
2. Led to a serious deterioration in health of the subject, that either resulted in
  - a. a life-threatening illness or injury, or
  - b. a permanent impairment of a body structure or a body function, or
  - c. in-patient hospitalization or prolongation of existing hospitalization, or
  - d. medical or surgical intervention to prevent life threatening illness or injury or permanent impairment to a body structure or a body function.
  - e. chronic disease
3. Led to fetal distress, fetal death or a congenital abnormality or birth defect.

**Note:** A planned hospitalization for a pre-existing condition, or a procedure required by the protocol without a serious deterioration in health, is not considered to be an SAE.

### 11.3 Device Deficiency

During the clinical study, the Principal Investigator will be responsible for reporting all device deficiencies on the applicable case report forms (CRFs) in the electronic data capture system.

A device deficiency is defined as an inadequacy of a medical device related to its identity, quality, durability, reliability, safety or performance, such as malfunction, misuse or use error and inadequate labeling. This includes the failure of the device to meet its performance specifications or otherwise perform as intended. Note: performance specifications include all claims made in the labeling of the device.

A device malfunction is the failure of a device to meet its performance specifications or otherwise perform as intended, when used in accordance with the instructions for use or protocol.

## 11.4 Device Relationship

Determination of whether there is a reasonable possibility that an investigational product or device under investigation caused or contributed to an AE is to be **determined by the Investigator** and recorded on the appropriate CRF form. Determination should be based on the assessment of temporal relationships, evidence of alternative etiology, medical/biologic plausibility and patient condition (pre-existing condition).

## 11.5 Unanticipated (Serious Adverse) Device Effect (USADE)

Unanticipated serious adverse device effect (USADE) refers to any serious adverse effect on health or safety or any life-threatening problem or death caused by, or associated with, a device, if that effect, problem or death was not previously identified in nature, severity, or degree of incidence in the investigational plan or application (including a supplementary plan or application), or any other unanticipated serious problem associated with a device that relates to the rights, safety, or welfare of subjects.

## 11.6 Adverse Event and Device Deficiency/Device Malfunction Reporting

Safety surveillance and reporting starts as soon as the patient met all enrollment requirements for the study. Adverse events will not be collected for screen failure subjects. Safety surveillance and reporting will continue until sites perform the last follow-up visit, the subject concludes participation in the clinical investigation, or the subject withdraws from the clinical investigation. Sites will collect all adverse event data, including deaths and device deficiency data throughout the period defined above and will report these events to the Sponsor on a CRF. Sites should update additional information regarding an adverse event on the appropriate CRF.

Unchanged, chronic, non-worsening or pre-existing conditions are not AEs and should not be reported.

The Sponsor will provide an offline form to allow the investigator to report SAEs in the event the entry cannot be made in the electronic data capture (EDC) system. This does not replace the EDC reporting system. Sites must still enter all information in the EDC system as soon as feasible.

Non-cardiac related laboratory values collected in the study that are abnormal will not be considered AEs unless:

1. the investigator determined that the value is clinically significant,
2. the abnormal lab value required intervention, or
3. the abnormal lab value required subject withdrawal from the clinical investigation.

Clinical Site	Reporting timelines
All Sites	
Sites must report SAE and Device Deficiency/Device Malfunction events to the Sponsor no later than 3 calendar days from the day the site personnel became aware of the event or as per the investigative site's local requirements, if the requirement is more stringent than those outlined.
 
Note: SAEs that occur prior to the subject's Portico ViV procedure are not required to be submitted/reported (refer to Table 3).

Sites must record the date the site staff became aware that the event met the criteria of an SAE in the source document. The Investigator will further report the SAE to the local EC according to the institution's EC reporting requirements.

All data including deaths and device deficiency data will be collected throughout the clinical study and will be reported to the Sponsor through the Electronic Data Capture (EDC) system. The Principal Investigator will record all reportable adverse events and device deficiencies on the appropriate CRFs. The Principal Investigator will report the event to the EC per their reporting requirements.

